2.0 Objectives

- Aim 1: To examine the feasibility and acceptability of the brief nurse-led intervention in BCS who have delayed initiation of AET or are hesitant to start (up to N=35) and refine the intervention using qualitative and quantitative feedback.

Hypothesis: The study will be feasible, defined by enrollment (rate>50%), retention (completion rate>70%) and attendance (≥70% of participants completing at least one session). The study will be acceptable as demonstrated by >75% of participants reporting average satisfaction scores greater than the mid-point of the Client Satisfaction Questionnaire (CSQ).

- Aim 2: To assess intervention-related changes in primary and secondary outcomes at one- and three-months post-baseline.

Hypothesis: Following the intervention, BCS will be more likely to have started their AET. We will explore changes in satisfaction with patient-physician communication, perceived social support, self-efficacy for symptom management, and quality of life.

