3.0 Research Subject Selection

3.1 Partial waiver of HIPAA Authorization

We request a partial waiver of HIPAA Authorization in order for our team to perform an initial screening process that requires review of the electronic medical record. This partial waiver is being requested to allow the research team to screen the oncology clinic schedules and identify potential study participants from a minimal chart review. In accordance with the DF/HCC policy: (1) this Waiver is being sought solely to review Protected Health Information as necessary to prepare a research protocol; (2) the Waiver will not include removing Protected Health Information from the Covered Entity by the researcher, and (3) the Protected Health Information for which we are requesting access is necessary for research purposes.

For individuals who provide verbal consent to participate in the study, we will obtain HIPAA authorization, as described in section 4.2 (Informed Consent Process).

Table 1. Inclusion Criteria
1. Female
2. Age 21 or older

3. Diagnosis of early-stage (Stage I-IIIB), hormone receptor-positive breast cancer
4. Recommended to start AET at least 3 weeks prior and not currently taking AET OR recommended to start AET in the future and reports hesitations to start AET as determined by a score of ≥ 4 (range =0-10) when asked "How hesitant are you about starting your recommended hormonal therapy? (0=Not at all hesitant and 10 = Extremely hesitant)"
5. Ability to read and respond in English or Spanish
6. Eastern Cooperative Oncology Group (ECOG) performance status ≤ 2
7. For at least 10 participants, identify as a member of a racial or ethnic minority community per self-report
Exclusion criteria
1. Uncontrolled psychosis, active suicidal ideation, psychiatric hospitalization within the past year
2. Cognitive impairment that prohibits participation in the study
3. Undergoing primary treatment for other cancer (i.e., advanced stage cancer)
4. Participating in a clinical trial involving AET
5. Diagnosis of Stage 0 (DCIS) breast cancer

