For patients meeting initial eligibility criteria and with clinician permission to approach, trained study staff will approach the patient at a clinic visit or by telephone to initiate the informed consent discussion and explain the study procedures. The study staff will first introduce the study to patients and ask if they have started taking their AET. If the patient indicates that they are not interested in the study, or are currently taking AET, study staff will collect the reason for refusal for the purposes of documentation and future study reporting. Depending on their reasons for refusal, study staff may request permission to re-approach some patients in the future, such as for later phases of this study.

For patients who engage via social media or are at other cancer institutions, they will self-report their age, diagnosis/staging, hormone receptor status, and ECOG score. We will aim to maximize recruitment of participants of a racial/ethnic minority via this method.

If the patient indicates that they are interested in the study and have not started taking their AET, the study staff

will screen the potentially eligible patient. Patients will be eligible if they have been recommended AET and have not started taking it within three weeks of the proposed start date, or if they are recommended to start AET in the future (e.g., post-radiation completion) and they have significant hesitations about starting AET. Hesitancy to start AET will be indicated by a score of ≥ 4 on the question, “how hesitant are you to start AET?” with 0 = not at all hesitant, and 10 = extremely hesitant. Once eligibility has been confirmed, the study staff will initiate the informed consent process verbally (if approached by telephone) or in-person (if approached in-clinic).

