5.2 Selection of Instruments

Instrument/Measure	Screening	Baseline (14-day window)	1-month follow-up (+/- 7 day)	3-month follow-up (+/- 7 day)
Chart Review	X			
Screening Questions (AET initiation)	X			
Demographics		X		
AET Initiation Question		X	X	X
Functional Assessment of Chronic Illness Therapy- Treatment Satisfaction-Patient Satisfaction (FACIT-TS-PS)		X	X	X
Beliefs about Medicines Questionnaire – Adjuvant Endocrine Therapy (BMQ-AET)		X	X	X
Multidimensional Scale of Perceived Social Support (MSPSS)		X	X	X
Functional Assessment of Cancer Therapy-Breast (FACT-B)		X	X	X
Hospital Anxiety and Depression Scale (HADS)		X	X	X
Self-Efficacy for Managing Symptoms Questionnaire (Self-Efficacy for Symptoms)		X	X	X
Measure of Current Status – Part A (MOCS)		X	X	X
Client Satisfaction Questionnaire (CSQ)			X	

Screening:

EHR Factors: The following information will be collected from participant EHR: MGH Main vs Affiliate site vs DFCI sites, demographic information, breast cancer stage, treatment (e.g., surgery, chemotherapy, radiation), AET type, approximate recommended AET start date, and medical or psychological co-morbidities.

AET Initiation questions: A question will be administered asking patients whether they have started taking their daily AET (yes vs. no). Patients who have not yet started AET will be considered eligible for study participation. Patients will also be asked how hesitant they are about starting their recommended hormonal therapy medication on a scale of 0-10.

Outcome Measures:

Demographics Questionnaire: Participants will self-report their age, gender, race/ethnicity, marital status, education level, and relationship status.

AET Initiation Question: This one item instrument will ask patients: At different times throughout your participation in this study, you may or may not be taking/have started taking your hormonal therapy. “At this time, are you currently taking your hormonal therapy (e.g., Tamoxifen, Anastrozole/Arimidex, Exemestane/Aromasin, Letrozole/Femara)?” Patients will self-report their initiation of endocrine therapy.

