9.2 Clinician Handout

Addressing Non-Initiation of Recommended Adjuvant Endocrine Therapy for Patients with a Culturally Informed Intervention

Study Rationale

- Up to 30% of BCS do not initiate AET as recommended.
- BCS of a racial or ethnic minority are disproportionately less likely to initiate AET.
- AET initiation is a modifiable health behavior with established predictors, with some being more salient for minority BCS.
- Interventions to improve initiation to AET are needed and should be culturally sensitive.
- Based on a qualitative study, we developed a culturally competent, two-session, nurse-led intervention to promote AET initiation in a diverse sample of early-stage, hormone receptor-positive BCS who have delayed initiation or have hesitations about initiating.

Study Specifics

- This is a single-arm pilot study in which up to 35 patients will be recruited to participate in a two-session intervention with purposeful recruitment of racial/ethnic minorities.
- We will aim to have one-third of the participants identifying as a racial or ethnic minority, in order to enroll a representative sample of experiences and concerns.
- The intervention consists of 2, one-hour sessions delivered over videoconferencing with a nurse practitioner. If necessary, these sessions can be delivered in person or via phone.
- All patients will be asked to complete assessments at baseline, 1-month, and 3-months after enrollment.

What Is Needed from You as the Clinician?

- Approve or deny study staff request to approach potentially eligible participants
- Refer patients you think may be eligible and a good fit for the study
- Provide care as usual

Patient Inclusion and Exclusion Criteria

- Female, age 21 or older, ability to read and respond in English or Spanish
- Diagnosis of early-stage (Stage I-IIIb), hormone-receptor positive breast cancer
- Recommended to start AET at least 3 weeks prior and not currently taking AET OR recommended to start AET in the future and reports hesitations to start AET as determined by a score of ≥ 4 (range =0-10) when asked "How hesitant are you about starting your recommended hormonal therapy? (0=Not at all hesitant and 10 = Extremely hesitant)"
- Eastern Cooperative Oncology Group (ECOG) performance status ≤ 2
- Does not have Stage 0 (DCIS) breast cancer
- May not have psychiatric or cognitive impairment
- May not have a psychiatric hospitalization within the past year

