9.5 Suggested Recruitment and Eligibility Phone Script

Hi, this is [Study Staff Name] calling from Massachusetts General Hospital/Dana-Farber Cancer Institute. Is this [Patient Name]?

A1. Self-referral call-back: Thank you for reaching out to our study team regarding the study. I would be happy to give you a brief overview of the study if you have a few minutes. Is now a good time?

IF YES: Continue to Section B.

IF NO: Is there a better time in the coming days I could give you a call back? [Continue to Section E.]

A2. Recruitment call: I am calling regarding a research study you might be eligible for that your oncologist, [provider name], thought you might be interested in. Is this a good time I could give you a brief overview of the study?

IF YES: Continue to Section B.

IF NO: Continue to Section E.

B. Study Description

This is a study about starting hormonal therapy, a type of medication that your oncologist recommended you take for breast cancer. This program consists of 2 sessions with a nurse over Zoom, to address any challenges or concerns you may be experiencing around beginning this medication. These visits would take place over a secure videoconferencing software Zoom. Does this sound like something you might be interested in?

IF YES: Continue to Section C.

IF NO: Continue to Section E.

C. Eligibility Pre-Screening

Thanks for your interest. To determine whether this study is a good fit for you, I am wondering, have you started taking the hormonal therapy prescribed to you by your oncologist?

IF YES: Continue to Section E.

IF NO: Continue in Section C.

On a scale of 0-10, with 0 indicating that you aren't at all hesitant and 10 indicating that you are extremely hesitant, how hesitant are you about starting your hormonal therapy?

IF ≥ 4 : Continue in Section D.

IF < 4 : Continue to Section E.

D. Consent Form Access and the Informed Consent Discussion

The next step is for us to go through the verbal consent process over the phone and I will send you a copy over email for your records.

IF YES: [Proceed to complete the verbal consent process]

IF NO: Okay, we can also complete the informed consent process through the mail. I will send you two copies of the consent form through the mail for you to sign both and send one back to me using a prepaid envelope I'll include. Additionally, I'll include the screening measures to verify your eligibility. [Collect address and continue to Section E]

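### Both suggested phone scripts apply the hesitancy cut-off of 4 to every woman, whereas Table 1 and section 4.1 apply it only to women with a future start

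*Combined protocol and SAP*

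**What the plan says.** Criterion 4 of Table 1 (section 3) reads "Recommended to start AET at least 3 weeks prior and not currently taking AET OR recommended to start AET in the future and reports hesitations", and then defines those hesitations as a score of at least 4 on a 0-10 scale.

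Section 4.1 states the same two routes in sentence form. The first is "Patients will be eligible if they have been recommended AET and have not started taking it within three weeks of the proposed start date"; the second is "or if they are recommended to start AET in the future (e.g., post-radiation completion) and they have significant hesitations about starting AET". The cut-off of 4 follows as the definition of hesitancy. The clinician handout (Appendix 9.2) repeats the first route without any score: "Recommended to start AET at least 3 weeks prior and not currently taking AET". Aim 1 in section 2.0 likewise joins delayed initiation and hesitancy with an 'or'. Section 5.2 treats not having started AET as making a patient eligible and adds "Patients will also be asked how hesitant they are about starting their recommended hormonal therapy medication on a scale of 0-10", with no threshold.

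The scripts work differently. Section C of Appendix 9.5 asks whether the woman has started AET and, if not, how hesitant she is. A score of 4 or more leads to the consent step in Section D. For lower scores the instruction is "IF < 4 : Continue to Section E", and Section E is the closing section that covers ineligible outcomes. The Spanish script (Appendix 9.6) routes the scores identically. Neither script asks for, or branches on, the recommended start date. Section 4.1 names these scripts as the means of assessing eligibility for contacts from the Rally portal.

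**The concern.** The protocol defines one population and its screening scripts select another. Two errors follow where a script is used as written:

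1. A woman at least three weeks overdue who scores 0-3 is eligible under Table 1 and section 4.1, but the call is closed.
2. A woman less than three weeks past her start date who scores 4 or more fits neither route, but is taken to consent.

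The first error loses eligible women before consent in a pilot of up to 35. The enrolled sample, and the one-month initiation rate that section 7.5 sets out to estimate, would then describe a somewhat narrower group than Table 1. The second error may mean that women consent and complete baseline before anyone finds that they do not qualify.

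**Working it through.** **Step 1. The two rules side by side.** Table 1 and section 4.1: eligible if (at least 3 weeks past the recommended start and not taking AET) or (future start and score of at least 4). Scripts: continue if not started and score of at least 4. With three start statuses and 11 possible scores there are 33 combinations.

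| Start status | Score 0-3 | Score 4-10 |
|---|---|---|
| At least 3 weeks past | Table 1: eligible. Script: closed out | Both: continue |
| Future start | Both: not eligible | Both: continue |
| Less than 3 weeks past | Both: not eligible | Table 1: not eligible. Script: to consent |

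The rules disagree in 4 + 7 = 11 combinations and agree in the other 22. The 4 are the first error and the 7 are the second.

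**Step 2. Could Table 1 mean the cut-off for both routes?** Read alone, its sentence might bear that. Section 4.1 does not: it attaches the hesitations to the clause on a future start. Aim 1 and section 5.2 agree with section 4.1.

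**Step 3. What else in the process could correct the script?** Section 4.1 takes the start date from the progress note for women found by EHR screening, and portal contacts are first checked in the EHR. There the information exists and only the branch is missing. Women from social media or outside institutions self-report age, diagnosis and stage, receptor status and ECOG score; start date is not on that list. Section 4.1 also says "Once eligibility has been confirmed, the study staff will initiate the informed consent process", but the script moves directly from the score to consent. The eligibility checklist is described in section 4.3 under registration, which follows consent and baseline. It may catch the second error late. It never sees women lost through the first.

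**Step 4. Illustrative size.** The documents give no hesitancy distribution, no overdue share and no share screened by script. All inputs here are assumptions:
- overdue share of eligible women, f = 0.5 to 1
- share of overdue women scoring 0-3, p = 0.10 to 0.30
- share screened by script, s = 0.5 to 1
- q = f × p = 0.05 to 0.30

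Turned away per 35 eligible, willing women = 35 × q × s:
- low: 35 × 0.05 × 0.5 = 0.9
- high: 35 × 0.30 × 1 = 10.5

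Suppose initiation in the low-scoring overdue women differs by 20 points (assumed) from the rest. Their share falls from q to q(1−s)/(1−qs), so the shift is 20 × [q − q(1−s)/(1−qs)]:
- q = 0.05, s = 0.5: 0.49 points
- q = 0.05, s = 1: 1.0 point
- q = 0.30, s = 0.5: 2.47 points
- q = 0.30, s = 1: 6.0 points

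The yardstick is section 7.5, which gives a maximum exact 95% interval width of 37.4% at 30 participants. Recalculation gives 37.41%, hence the half-width of 18.7 points.

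**Step 5. Enrolment criterion.** Section 1.3 reports 72% enrolment in a related adherence trial. Taking all women as overdue and scripted:
- counting all approached: 0.72 × 0.90 = 64.8%; 0.72 × 0.70 = 50.4%
- leaving those turned away out of the denominator: 0.648 / (1 − 0.072) = 69.8%; 0.504 / (1 − 0.216) = 64.3%

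All four exceed 50%. On the first count the line is reached at p = 1 − 0.50/0.72 = 30.6%, just above the assumed ceiling, so the 50.4% has almost no margin.

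**The case against.** The mismatch itself is hard to dispute; the case on the other side concerns its reach and weight.

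- **The scripts are only suggested, and only a pre-screen.** They ask nothing about stage, receptor status or exclusions, so other screening must take place. In-clinic approaches need not use them. This stands, and limits the problem to calls where the script is followed.
- **The second error is partly guarded.** Section 4.1 restricts approach to patients who meet initial criteria, the EHR supplies the start date for many, and the mail route in Section D of the script encloses screening measures. This stands for women with an accessible record. It does little for social-media and outside-institution contacts, and nothing for the first error.
- **Other recruitment material also speaks of hesitation.** Both flyers list doubts about starting, and two of the three social-media texts address worried women. This suggests that a general cut-off may have been intended, and that few women from those routes would score 0-3. But these are advertisements and do not set eligibility. The English portal advertisement mentions no hesitancy at all.
- **Weekly reports of ineligibility reasons (section 6.0) could reveal the losses.** They could, but nothing ensures that a woman already turned away is called back.
- **The magnitudes are assumed.** Correct. The top of the range needs every woman overdue, every call scripted and 30% scoring low. The 72% comes from a trial in women already taking AET. Women turned away need not shrink the final sample either, since recruitment can continue and section 4.1 cites at least 75 non-initiators. The chart reasons in section 1.3, worry over side effects and long-term harm, may also point to the low end.

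**Conclusion.** The concern holds. Both scripts apply a different eligibility rule from Table 1, section 4.1 and the handout, and give the wrong result in 11 of 33 combinations of start status and score. That conclusion rests on the text alone.

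The size is unknown. The ranges above depend entirely on assumed shares and an assumed 20-point difference in initiation. They show neither a shift beyond the planned precision nor a changed enrolment conclusion, and they cannot rule out a larger effect if the true shares lie outside those assumed. The point should be corrected because a tool named for assessing eligibility contradicts the criteria, in both languages, and the correction is easy.

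**What to change.** Reconcile Appendices 9.5 and 9.6 with Table 1 and section 4.1. The sponsor must decide which rule is intended.

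**If Table 1 stands**, after the answer that AET has not been started, confirm the recommended start date (from the EHR, or by asking women recruited through social media or outside institutions), then branch:
1. At least 3 weeks past: record the hesitancy score without a cut-off and continue to Section D.
2. Future start: apply the cut-off of 4.
3. Less than 3 weeks past: not yet eligible under Table 1; log this and ask permission to re-contact. Section 4.1 already lets staff ask some patients for permission to re-approach.

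**If the cut-off was meant for all women**, leave the score routing in place and change Table 1, section 4.1, the handout and the 'or' in Aim 1.

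The first option costs one question with its branch in two scripts, in two languages, and an IRB amendment. The second costs text changes in four places and an amendment. The flyers and social-media texts can be checked against the chosen rule at the same time.

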9.6 Suggested Recruitment and Eligibility Phone Script - Spanish

Hola, mi nombre es [Study Staff Name] estoy llamando por parte de Massachusetts General Hospital/Dana-Farber Cancer Institute. Es usted [Patient Name]?

A1. Llamada de Autorreferencia: Muchas gracias por contactar a nuestro equipo sobre nuestro estudio. Si tiene algunos minutos, me encantaría darle un resumen corto sobre nuestro estudio. ¿Está disponible?

SI DICE “Sí”: Continúe a la Sección B.

SI DICE “No”: ¿Tendría algún momento en los próximos días en el pueda contactarme otra vez con usted? [Continúe a la Sección E.]

A2. Llamada de Reclutamiento: Estoy llamando sobre un estudio en el puede ser elegible para participar, y que su oncólogo, [provider name], pensó que a lo mejor le pudiera interesar. Si tiene algunos minutos, me encantaría darle un resumen corto sobre nuestro estudio. ¿Está disponible?

SI DICE “Sí”: Continúe a la Sección B.

SI DICE “No”: Continúe a la Sección E.

B. Descripción del Estudio

Este estudio esta relacionado con el comienzo del tratamiento hormonal, un tipo medicación que su oncólogo le ha recomendado que tome para cáncer de mama. Este programa incluye 2 sesiones con una enfermera a través de Zoom, individuales y culturalmente informadas para enfrentar cualquier desafío o preocupaciones que pueda estar teniendo al comenzar a tomar este medicamento. Estas visitas se realizarían a través de un software de videoconferencia segua utilizando Zoom. ¿Le interesaría participar?

SI DICE “Sí”: Continúe a la Sección C.

SI DICE “No”: Continúe a la Sección E.

C. Preselección de Elegibilidad

Muchas gracias por su interés. ¿Para determinar si este estudio es una buena opción para usted, le quería preguntar si usted ha empezado a tomar el medicamento de tratamiento hormonal que le prescribió su oncólogo?

SI DICE “Sí”: Continúe a la Sección E.

SI DICE “No”: Continúe a la Sección C.

En una escala del cero al diez, cero indicando que no tiene duda en absoluto y diez indicando que está sumamente indecisa ¿Qué tan indecisa está usted de comenzar su tratamiento hormonal?

Si ≥ 4 : Continúe a la Sección D.

Si < 4 : Continúe a la Sección E.

D. Acceso al Formulario de Consentimiento y Discusión Sobre el Consentimiento Informado

El próximo paso es de que revisemos el formulario de consentimiento y le enviaré una copia por correo electrónico para sus registros.

SI DICE “Sí”: Continúe en la Sección D. [Proceed to complete the verbal consent process]

SI DICE “No”: No hay problema, también se puede completar este proceso por el correo. Le mandare dos copias del formulario por el correo para que usted firme las dos y me mande una copia devuelta usando un sobre prepagado que también le enviare. Adicionalmente, incluiré los requisitos de selección para verificar su elegibilidad. [Obtener su Dirección y Continúe a la Sección E]

E. Ningún Interés, Rechazo, Prefiere Copia del Consentimiento en Papel, No es elegible.
Muchísimas gracias por su tiempo. Si usted tiene alguna preocupación o pregunta acerca del estudio, por favor no dude en contactarnos.

